10. DISPOSITION AND WITHDRAWALS

All patients who provide informed consent will be accounted for in this study. A tabulation of patient disposition will be presented for the APSS including number enrolled, number in each patient population, and number of withdrawals, including reasons for withdrawal as documented on the eCRF.

Protocol deviations as reported on the eCRF will be will be presented as part of the listings including the deviation category, description and type.

The number of patients who fail to meet each inclusion criterion or meet any exclusion criterion (including angiographic criterion) will be presented for the FAS.

11. Demographic and other Baseline Characteristics

Demographic data and other baseline characteristics will be presented for the FAS.

The following demographic and other baseline characteristics will be reported for this study:

- Age (years) calculated relative to the date of enrollment
- Age groups: < 65 years, ≥ 65 years
- Gender (with childbearing potential for females)
- Race
- Ethnicity
- · Weight (kg)
- · Height (cm)
- BMI (kg/m2)
- Systolic Blood Pressure (mmHg)
- Diastolic Blood Pressure (mmHg)
- · Heart Rate (bpm)

Document: T:\PROJ\Medinol\CXA27472\06 Biostatistics\Documentation\SAP\Final

1.0_08Aug2018\JNIR01_SAP_Final V1.0_08Aug2018.docx

Author: [name] Version Number: Final V1.0 Version Date: 08Aug2018

Template No: CS_TP_BS016 Revision 4 Reference: CS_WI_BS005

Effective Date: 01Apr2016

Copyright © 2009, 2010, 2012, 2016 Quintiles Transnational Corp. All rights reserved.

11.1. DERIVATIONS

• BMI (kg/ m2) = weight (kg)/ height (m)2

12. MEDICAL HISTORY

The following medical history information will be presented for the FAS:

- Acute coronary syndrome (Y/N)
- Previous myocardial infarction (Y/N)
- History of angina pectoris (Y/N)
 - CCS class (I, II, III, IV)
- Previous PCI (Y/N)
 - Target vessel
 - Target lesion treated
 - Non-target vessel
 - Method of treatment (PTCA, stenting, other)
- Previous CABG (Y/N)
 - Target vessel
 - Non-target vessel
- LVEF assessed prior to index procedure (Y/N)
 - LVEF (%)
- Family history of premature coronary disease (Y/N)
- Diabetes mellitus (Y/N)
 - Type (I, II)
 - Controlled by (insulin, oral medications, diet/untreated)
- Hypertension (Y/N)
 - Medically treated (Y/N)
- Hyperlipidemia (Y/N)
 - Medically treated (Y/N)
- Previous TIA (Y/N)
- Previous CVA (Y/N)
- Congestive Heart Failure (Y/N)
 - NYHA Class (I, II, III, IV)
- Vascular Disease (Y/N)
- Atrial fibrillation (Y/N)
- History of Bleeding complications (Y/N)
 - BARC Classification (type 0, 1, 2, 3, 4, 5)
- Renal Insufficiency (Y/N)

Document: T:\PROJ\Medinol\CXA27472\06 Biostatistics\Documentation\SAP\Final

1.0_08Aug2018\JNIR01_SAP_Final V1.0_08Aug2018.docx

Author: [name] Version Number: Final V1.0 Version Date: 08Aug2018

Template No: CS TP BS016 Revision 4 Reference: CS WI BS005

 History of Smoking/Alcohol (Smoking status, average number of cigarettes per day, number of years smoking, alcohol abuse status)

Other medical/surgical history will be coded using the Medical Dictionary for Regulatory Activities (MedDRA) central coding dictionary, Version 21.0 or a later version. The other medical/surgical history will be summarized by system organ class (SOC) and preferred term (PT) within system organ class for the FAS, with SOC sorted alphabetically and PT within SOC by descending incidence. Investigator verbatim as well as preferred terms and system organ class will be included in the listings.

13. STUDY STENT PROCEDURAL INFORMATION

Site reported procedure characteristics will be summarized on patient level for the FAS and will include the following:

- Any Intervention: pre-dilatation of at least one target lesion performed, any atherectomy, cutting/scoring balloon, any thrombectomy/aspiration, one or more stents implanted in target vessel
- Patients with stents implanted in target vessel (number of stents implanted, number of patients with overlapping stents, total stents length implanted in mm)
- Any post-stent dilatation
- · Number of diseased vessels
- Multiple diseased vessels (1, 2, 3, 4)
- Location of diseased vessels (LAD/Diag, LCX/OM/Ramus, RCA/RPDA/RPL, Protected LM, Bypass vein or artery)
- · Number of treated lesions
- Multiple lesions treated (1, 2, 3, 4)
- · Bailout procedure
- Any procedural complications
- Any staged procedure planned
- Procedure duration in minutes calculated as procedure end date/time procedure start date/time + 1
- Number of hospital nights calculated as hospital discharge date procedure start date

14. TARGET LESION CHARACTERISTICS

The following site reported target lesion characteristics will be summarized on lesion level for the FAS:

- Location of lesion
- % Diameter stenosis pre procedure
- Reference Vessel Diameter in mm
- Lesion length in mm
- Pre-Dilatated

Balloon Length, mm

Document: T:\PROJ\Medinol\CXA27472\06 Biostatistics\Documentation\SAP\Final

1.0_08Aug2018\JNIR01_SAP_Final V1.0_08Aug2018.docx

Author: [name] Version Number: Final V1.0 Version Date: 08Aug2018

Template No: CS TP BS016 Revision 4 Reference: CS WI BS005

Effective Date: 01Apr2016

Copyright © 2009, 2010, 2012, 2016 Quintiles Transnational Corp. All rights reserved.

- Nominal Diameter,mm
- Maximum Balloon Pressure, atm
- FFR performed (Y/N)
 - Hyperemic FFR
- Number of stents per lesion (1, 2, 3, >3, more than one stent implanted)
- · Total stent length per lesion, mm
- Maximum stent balloon pressure, atm (For each lesion, the stent with the maximum pressure will be reported)
- Maximum stent diameter, mm (For each lesion, the stent with the maximum stent diameter will be reported)
- · Stent post dilated
- % Diameter stenosis (final)

15. EFFICACY OUTCOMES

Per protocol, patients may have multiple target lesions treated. For patient level endpoints, only one lesion per patient is required to meet the criteria for the endpoint. All endpoints are summarized on a patient level, except when noted.

For the binary primary and selected secondary endpoint event rates to be calculated, the denominator will include only patients who have either had the event by the time of interest (end of the visit window), or had follow-up (starting from the beginning of the visit window) for the endpoint. Visit windows are defined in Section 7.5.

For example, at the 1 year analysis (day 365), only patients who have either had the event by day 365 + 14 = 379 or had follow-up up to day 365 - 30 = 335 will be included in the analysis for the endpoint. In this example, if a patient has an event at day 10 post procedure, the patient will be included in the 1 year analysis and counted as an event. However, if a patient drops out of the study at day 10 post procedure without an event (e.g., due to withdrawal of consent) the patient will not be included in the analysis.

All events as reported by the CEC as well as by the sites will be listed.

15.1. PRIMARY EFFICACY

15.1.1. PRIMARY EFFICACY VARIABLE & DERIVATION

The primary efficacy variable is target lesion failure (TLF) at 12 months post-procedure defined as the composite of cardiac death, target vessel related myocardial infarction (MI), or clinically-driven target lesion revascularization (TLR) as adjudicated by the CEC. This endpoint includes spontaneous MIs and peri-procedural MIs adjudicated per the Universal definition [1] and SCAI definition [2], respectively.

Document: T:\PROJ\Medinol\CXA27472\06 Biostatistics\Documentation\SAP\Final

1.0_08Aug2018\JNIR01_SAP_Final V1.0_08Aug2018.docx

Author: [name] Version Number: Final V1.0 Version Date: 08Aug2018

Template No: CS TP BS016 Revision 4 Reference: CS WI BS005

Effective Date: 01Apr2016

Copyright © 2009, 2010, 2012, 2016 Quintiles Transnational Corp. All rights reserved.

15.1.2. PRIMARY ANALYSIS OF PRIMARY EFFICACY VARIABLE

The primary objective of this study is to measure the non-inferiority of JNIR Target Lesion Failure at 12 months (TLF₁₂) to the BIONICS TLF₁₂.

The trial defines the statistical null hypothesis as

 H_{Null} : TLF_{12} (JNIR) > TLF_{12} (BIONICS) + δ

 $H_{Alternative}$: TLF_{12} (JNIR) $\leq TLF_{12}$ (BIONICS) + δ

or in terms of absolute event-rate difference

 H_{Null} : TLF_{12} (JNIR) - TLF_{12} (BIONICS) > δ

H_{Alternative}: TLF₁₂ (JNIR) - TLF₁₂ (BIONICS) $\leq \delta$

where δ =0.05 is the margin of non-inferiority (refer to Section 8.5).

The primary efficacy analysis will be performed for the FAS. Only patients with appropriate follow up (>=335 days post procedure) or who experienced the primary endpoint by the end of the 365 day visit window (day 379) will be included.

A comparison of the proportion of patients with TLF at 12 months will be performed using the Farrington-Manning test of non-inferiority for two binomial proportions with a non-inferiority margin of δ =0.05 at the 0.1 level of significance (one-sided) [3].

The Farrington-Manning test statistic will be calculated as follows:

$$\tau = \frac{\text{TLF}_{12} \text{ (JNIR)} - \text{TLF}_{12} \text{ (BIONICS)} - \delta}{\sqrt{\frac{\text{TLF}_{12} \text{ (JNIR)}[1 - \text{TLF}_{12} \text{ (JNIR)}]}{N(\text{JNIR})} + \frac{\text{TLF}_{12} \text{ (BIONICS)}[1 - \text{TLF}_{12} \text{ (BIONICS)}]}{N(\text{BIONICS})}}$$

where N(JNIR) and N(BIONICS) are the number of patients from the JNIR trial and BIONICS trial, respectively.

Propensity score matching will identify a covariate-unbiased population of patients between the JNIR and BIONICS patient population. To maximize power and take advantage of the large BIONICS study, 4:1 matching will be done. This covariate-unbiased population will be used to calculate TLF_{12} (BIONICS) and N(BIONICS) in the Farrington-Manning test statistic.

The probability a patient (x) belongs to JNIR versus BIONICS, conditional on a set of potential confounding covariates (C), defines the propensity score $\rho(x \mid C)$. Logistic regression will model this probability as

$$\rho(\mathbf{x} \mid \mathbf{C}) = \mathrm{logit}^{-1} \left(\sum_{c \in C} c \right)$$

where $logit^{-1}(x) = \frac{1}{1 + e^{-x}}$.

Matching of patients from JNIR to patients from BIONICS will be done using the following covariates which

Document: T:\PROJ\Medinol\CXA27472\06 Biostatistics\Documentation\SAP\Final

1.0_08Aug2018\JNIR01_SAP_Final V1.0_08Aug2018.docx

Author: [name] Version Number: Final V1.0 Version Date: 08Aug2018

Template No: CS TP BS016 Revision 4 Reference: CS WI BS005

Effective Date: 01Apr2016

Copyright © 2009, 2010, 2012, 2016 Quintiles Transnational Corp. All rights reserved.

are known to confound the relationship between study-stent and outcome:

Covariates considered in propensity-score matching:

Clinical Parameters (as captured in the eCRF):

- Age
- Gender
- Prior MI
- · Medically treated diabetes Mellitus
- Prior Revascularization (Either previous PCI or previous CABG captured on the medical history eCRF form)
- Acute Coronary Syndrome

Pre-procedure Angiographic Parameters (as reported in the Quantitative Coronary Angiography (QCA) data):

- · Diameter Stenosis
- Reference Vessel Diameter
- Calcification
- TIMI Flow (Pre-procedure)
- Tortuosity
- SYNTAX Score
- Lesion located at LAD

After each patient in both JNIR and BIONICS has received a propensity score, these two groups will be combined and partitioned into propensity score quintiles.

Finally, each JNIR patient in quintile x is matched with 4 random BIONICS patients from the same quintile x. If no remaining BIONICS patients are left to match with JNIR patients in one of the five quintiles, the next closest quintile will be used to choose a BIONICS patient.

The clinical and angiographic covariates used in the propensity-score matching will be summarized for the FAS by treatment group.

The proportion of TLF as well as proportions of cardiac death, target vessel related MI and clinically-driven TLR at 12 months along with the corresponding exact 95% CIs will be presented for the JNIR group and matched BIONICS group. The difference in proportion will be reported. Farrington-Manning one-sided p-value and upper bound of the one-sided 90% CI of the difference in proportion between JNIR and matched BIONICS groups will be presented.

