7.2 Analysis of Efficacy

7.2.1 Primary Endpoint

Primary Endpoint hypothesis

This trial measures the non-inferiority of JNIR Target Lesion Failure at 12 months (TLF_{12}) to the BIONICS TLF_{12} .

The trial defines the statistical null hypothesis as H_{Null} : TLF₁₂ (JNIR) > TLF₁₂ (BIONICS) + δ $H_{Alternative}$: TLF₁₂ (JNIR) \leq TLF₁₂ (BIONICS) + δ

or in terms of absolute event-rate difference

H_{Null}: TLF₁₂ (JNIR) - TLF₁₂ (BIONICS) > δ H_{Alternative}: TLF₁₂ (JNIR) - TLF₁₂ (BIONICS) $\leq \delta$

where δ is the margin of non-inferiority.

Measured statistic

Farrington-Manning methodology estimates the difference in TLF_{12} as TLF12 (INIR) – TLF12 (BIONICS) – 8

$$\tau = \frac{\Gamma LF12 (JNIR) - \Gamma LF12 (BIONICS) - 6}{\sqrt{\frac{T LF12 (JNIR)[1 - T LF12 (JNIR)]}{N(JNIR)} + \frac{T LF12 (BIONICS)[1 - T LF12 (BIONICS)]}{N(BIONICS)}}$$

where N(x) is the number of x patients.

Propensity-score matching

Propensity score matching will identify a covariate-unbiased population of patients between the JNIR and BIONICS patient population. The probability a patient (x) belongs to JNIR versus BIONICS, conditional on set of potential confounding covariates (C), defines the propensity score $\rho(x | C)$. Logistic regression will model this probability as

$$\rho(x \mid \mathcal{C}) = \operatorname{logit}^{-1} \left(\sum_{c \in \mathcal{C}} c \right)$$

where $logit^{-1}(x) = \frac{1}{1 + e^{-x}}$.

We will match patients from JNIR to patients from BIONICS using the following covariates known to confound the relationship between study-stent and outcome:

Covariates considered in propensity-score matching:

Clinical Parameters: Age Gender Prior MI Diabetes Mellitus Prior Revascularization Acute Coronary Syndrome Angiographic Parameters: Diameter Stenosis Reference Vessel Diameter Calcification TIMI Flow (Pre-procedure) Tortuosity SYNTAX Score Lesion located at LAD

After each patient in both JNIR and BIONICS has received a propensity score, these two groups will be combined and partitioned into propensity score quintiles.

Finally, we will match each JNIR patient in quintile x with a random BIONICS patient from the same quintile x. If no remaining BIONICS patients are left to match with JNIR patients in one of the five quintiles, we use the next closest quintile to choose a BIONICS patient.

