7.5 Sample Size Considerations

Power

The Farrington-Manning test, with a TLF_{12} event-rate of 0.058, margin of 0.05, Type I error α of 0.10, and propensity-score matching 1 JNIR to 4 BIONIC patients provides enrollment of 100 subjects will provide 80% power expecting a 5% loss to follow up. We derive the 0.058 event rate from a sample-weighted average of the same 8 related trials used to design BIONICS: SPIRIT (III/IV), PLATINUM, RESOLUT (All Comers / US), TWENTE, and COMPARE (I/II). A margin of 0.05 (5%) , 1.5 times that of BIONICS, leverages a reasonable clinical threshold with safety concerns over sample size. Likewise, propensity-score matching every one JNIR patient to 4 BIONICS patients allows higher power without a higher burden on enrollment.

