8.5. ACTIVE-CONTROL STUDIES INTENDED TO SHOW NON-INFERIORITY OR EQUIVALENCE

JNIR01 is aimed at assessing TLF at one year with the MedJ-01 stent in a Japanese patient population to show non-inferiority of JNIR01 TLF₁₂ to the BIONICS TLF₁₂.

The non-inferiority margin will be set to 0.05 (5%). This margin, 1.5 times that of BIONICS, leverages a reasonable clinical threshold with safety concerns over sample size.

If the one-sided 90% confidence interval for the upper bound of the difference (JNIR01 TLF₁₂ minus BIONICS TLF₁₂) is less than this pre-specified non-inferiority margin, then the null hypothesis is rejected.

Details of the statistical method used to test non-inferiority are given in Section 15.1.

Document: T:\PROJ\Medinol\CXA27472\06 Biostatistics\Documentation\SAP\Final

1.0_08Aug2018\JNIR01_SAP_Final V1.0_08Aug2018.docx

Author: [name] Version Number: Final V1.0 Version Date: 08Aug2018

Template No: CS TP BS016 Revision 4 Reference: CS WI BS005

Effective Date: 01Apr2016

Copyright © 2009, 2010, 2012, 2016 Quintiles Transnational Corp. All rights reserved.

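### The statistic printed as Farrington-Manning is the unrestricted Wald statistic; if it is programmed as printed, the 10% type I error of the only formal test becomes about 13%

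*SAP*

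**What the plan says.** SAP 15.1.2 chooses the "Farrington-Manning test of non-inferiority for two binomial proportions", cites its source paper, and applies it with a margin of 0.05 "at the 0.1 level of significance (one-sided". It then writes "The Farrington-Manning test statistic will be calculated as follows" and gives, in substance:

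τ = (p_J − p_B − δ) / √[ p_J(1 − p_J)/N_J + p_B(1 − p_B)/N_B ]

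Here p_J and p_B are the 12-month TLF rates in JNIR and BIONICS. The SAP adds that the matched population supplies the BIONICS rate and "N(BIONICS) in the Farrington-Manning test statistic". Protocol 7.2.1 prints the same expression, introduced by "Farrington-Manning methodology estimates the difference in".

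For reporting, the SAP promises the "Farrington-Manning one-sided p-value and upper bound of the one-sided 90% CI of the difference in proportion". SAP 8.5 makes that bound the decision rule but names no method for it. SAP 7.6 specifies SAS 9.4 or higher, with no procedure or option. Protocol 7.5 bases its 80% power claim on the Farrington-Manning test.

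**The concern.** The defining feature of Farrington-Manning is its variance: the two rates are estimated by maximum likelihood under the constraint p_J − p_B = δ. The printed denominator has no constrained estimates. It uses the same rates as the numerator, so it is the Wald statistic under another name.

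The difference matters because JNIR is small and TLF is uncommon. When JNIR happens to have few events, the observed-rate variance is too small and τ becomes too negative. Those are the samples that pass.

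This is the only hypothesis formally tested (SAP 7.5 and 8.4), and its level is already 10% one-sided. SAP section 5 has a separate organisation run the analysis to the SAP's specifications. The printed formula is the most explicit of these, so programming it is a realistic outcome. A standard routine for the named test could then reach the opposite conclusion on the same data.

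**Working it through.** **Inputs.** Protocol 7.5 gives "event-rate of 0.058, margin of 0.05, Type I error α of 0.10, and propensity-score matching 1 JNIR to 4 BIONIC patients", with 100 enrolled and 5% loss to follow-up. Hence N_J = 95 and N_B = 4 × 95 = 380. The one-sided critical value is z₀.₉₀ = 1.2816.

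**The plan's own figure: 80% power.** Normal approximation, both rates 0.058:

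- True standard error: √[0.058 × 0.942 × (1/95 + 1/380)] = 0.02681.
- Printed (Wald) formula: Φ(0.05/0.02681 − 1.2816) = Φ(0.583) = 72.0%.
- Farrington-Manning: the restricted rates are 0.1021 and 0.0521, so the null standard error is √[0.1021 × 0.8979/95 + 0.0521 × 0.9479/380] = 0.0331. Power is Φ((0.05 − 1.2816 × 0.0331)/0.02681) = 61.2%.
- Exact power by full enumeration is 70.0% (printed) and 64.4% (Farrington-Manning).

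Neither variance reproduces 80%, so the power statement cannot show which statistic was meant. The shortfall is a separate matter.

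**Type I error.** Every pair of event counts was enumerated under two independent binomials at p_J = p_B + 0.05, rejecting when the statistic is ≤ −1.2816. Only the variance differs between the columns.

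| BIONICS rate (95/380) | Printed formula | Farrington-Manning |
|---|---|---|
| 3% | 13.7% | 9.9% |
| 4% | 13.2% | 10.1% |
| 5% | 13.0% | 10.2% |
| 5.8% (planning rate) | 12.8% | 10.1% |
| 8% | 12.3% | 9.9% |

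A simulation of 2,000,000 trials at the planning rate also gave 12.8% for the printed formula. Sensitivity:

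- At 100/400 and 5.8%, the figures are 12.7% and 10.1%.
- For JNIR n from 90 to 100 with 4:1 matching at 5.8%, the printed formula gives 12.6–13.8% (mean 13.1%) and Farrington-Manning 9.3–10.1%.
- For assumed BIONICS rates from 1% to 10% at 95/380, the printed formula runs from 16.7% down to 12.1%; Farrington-Manning stays within 9.0–10.2%.

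**Disagreement between the tests at 95/380.** With both true rates 5.8%, 5.6% of trials pass by the printed formula and fail by Farrington-Manning; the reverse does not occur. At the null boundary (10.8% versus 5.8%) the figure is 2.7%, which is the gap between 12.8% and 10.1%.

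For BIONICS counts from 8 to 35, the largest passing JNIR count differs by one event at 8, 9, 10, 14, 15, 19, 20, 24, 25, 29, 30, 34 and 35. At the other counts in that range it is the same. The expected count is 380 × 0.058 = 22, so several of the discordant counts are likely results.

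**Worked example: JNIR 6/95, BIONICS 20/380.** The observed rates are 0.0632 and 0.0526. The numerator is 0.0105 − 0.05 = −0.0395.

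- Printed formula: SE = √[0.0632 × 0.9368/95 + 0.0526 × 0.9474/380] = 0.0275, z = −1.44, p = 0.075. The upper bound is 0.0105 + 1.2816 × 0.0275 = 0.046, below 0.05: non-inferior.
- Farrington-Manning: the restricted rates are 0.0981 and 0.0481, SE = √[0.0981 × 0.9019/95 + 0.0481 × 0.9519/380] = 0.0324, z = −1.22, p = 0.112: non-inferiority not shown.

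**The case against.** The strongest reply is that the inflation is conditional. The SAP names the test, cites its source and promises a Farrington-Manning p-value. An analyst who runs a standard routine for that test keeps the error near 10%, and the defect is then only a conflict between name and formula. This is true, and it limits the claim: 12.8% applies if the formula is followed. It does not rescue the text, because the SAP would then prescribe a calculation that nobody performs.

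A second reply is that the symbols carry no marks to separate true, observed and restricted rates, and that saying the matched patients supply the BIONICS rate identifies the patients, not the estimator. This lowers certainty only slightly. Numerator and denominator use the same symbols, neither document mentions a restricted estimate, and the formula appears in both.

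Third, the effect is modest: about 2.7 percentage points, and never more than one JNIR event in the passing threshold at BIONICS counts from 8 to 35. That is fair. But the shift always favours declaring non-inferiority, and it affects the trial's single formal test.

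Finally, all these figures assume independent binomials, whereas the comparator is selected by propensity-quintile matching. This caveat stands for both tests.

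**Conclusion.** The concern holds. SAP 15.1.2 and protocol 7.2.1 name Farrington-Manning but print the Wald statistic, and nothing else in either document settles which governs. Followed as printed, the primary test has a type I error of 12.8% against a nominal 10% at the planning inputs (12.3–13.7% for BIONICS rates of 3–8%). Farrington-Manning gives 10.1% (9.9–10.2%).

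The result rests on 95 and 380 evaluable patients, the 0.05 margin, independent binomial counts, and the formula being programmed with observed rates. It should be corrected before the primary analysis. In an open-label trial, the choice between the two statistics could otherwise be made when both p-values can be known.

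**What to change.** In SAP 15.1.2 and protocol 7.2.1, replace the denominator with √[ p̃_J(1 − p̃_J)/N_J + p̃_B(1 − p̃_B)/N_B ], where p̃_J and p̃_B are the maximum-likelihood rates under p̃_J − p̃_B = 0.05. Leave the observed rates in the numerator. Name the procedure, for example SAS PROC FREQ with RISKDIFF and the options NONINF, MARGIN=0.05 and METHOD=FM. In SAP 8.5 and 15.1.2, state that the one-sided 90% upper bound is obtained by inverting the same score test, so that p-value and bound give one decision.

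The cost is a text correction and one software option. Exact power at 95/380 falls from 70.0% to 64.4%, and the power statement in protocol 7.5 should acknowledge this. By the normal approximation, 80% power with Farrington-Manning would need 161 evaluable JNIR patients (161/0.95, or 170 enrolled).

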6 DESIGN OF THE CLINICAL INVESTIGATION

6.1 General

6.1.1 Description of Trial

The JNIR Trial will enroll approximately 100 subjects with a wide spectrum of PCI indications (stable angina as well as ACS, including subacute STEMI (>72 hours since first hospital presentation).

This is a prospective, multi-center, single-arm, open label clinical trial. Lesions planned to be treated must be declared and recorded at time of enrollment.

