6.4.6 Study Stent Use

Prior to use, the study stent will be inspected and prepared according to the applicable Instructions for Use. **Note**: Refer to the MedJ-01 IFU in the trial's Site Binder.

- There is no limit to individual lesion length. However, the total planned stenting in the coronary tree cannot exceed 100 mm. A maximum of two target vessels may be treated with study stents with a maximum of two lesions per vessel. Two lesions separated by less than 10 mm that can be covered with a single stent are considered as one lesion
- If more than one target lesion is treated, all lesions must receive the study stent.
- If more than one lesion in the same epicardial vessel is treated, it is recommended that stenting be initiated distally and progress proximally.
- Overlapping stents are allowed with the investigational device (MedJ-01). It is recommended that the distal stent should be deployed first, followed by deployment of the proximal stent, to reduce the risk of dislodging the proximal stent.
- Stent sizing should follow a stent: artery ratio of 1.1:1 per operator's visual estimate.
- Brachytherapy must NOT be performed in conjunction with the baseline procedure.
- Post-dilation is strongly recommended, and when performed should only be performed with balloon lengths that fit within the boundaries of the stent. Do not exceed the rated burst pressure as indicated in the product labeling of the study stents. The vessel size and lesion length should be assessed after post-dilation. An optimal stent result is final diameter stenosis of <20% by operator's visual estimate.

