8. STATISTICAL CONSIDERATIONS

8.1. ADJUSTMENTS FOR COVARIATES AND FACTORS TO BE INCLUDED IN ANALYSES

No adjustments for covariates are planned for the statistical analyses.

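### The propensity model does not directly include the number or length of target lesions, although one failing lesion out of up to four makes the patient a TLF case

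*SAP*

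**What the plan says.** The primary test compares the 12-month TLF proportion in JNIR with that in BIONICS patients matched 4:1 on a propensity score. Under "Covariates considered in propensity-score matching", SAP 15.1.2 lists:

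- six clinical items: age, gender, prior MI, medically treated diabetes, prior revascularization and ACS;
- seven angiographic items: diameter stenosis, reference vessel diameter, calcification, pre-procedure TIMI flow, tortuosity, SYNTAX score and LAD location.

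Protocol 7.2.1 has the same thirteen, except that it does not restrict diabetes to medically treated cases.

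On how many lesions a patient may have, Protocol 6.4.6 says: "A maximum of two target vessels may be treated with study stents with a maximum of two lesions per vessel". It adds: "There is no limit to individual lesion length", subject to 100 mm of total planned stenting. On the endpoint, SAP 15 says: "For patient level endpoints, only one lesion per patient is required to meet the criteria for the endpoint".

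Both missing items are recorded in JNIR. Protocol 6.1.1 requires: "Lesions planned to be treated must be declared and recorded at time of enrollment". SAP 13 tabulates "Number of treated lesions" and SAP 14 tabulates "Lesion length in mm", both site-reported.

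Nothing later covers the gap. SAP 8.1 states: "No adjustments for covariates are planned for the statistical analyses". The only sensitivity analysis of the primary endpoint repeats it in the per-protocol set (SAP 15.1.3). Balance is to be summarized only for the covariates used in the matching.

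**The concern.** JNIR is a single-arm study compared with an external cohort, so the matching has to do the work that randomization would otherwise do. Under an any-lesion rule, the number of target lesions sets how many chances each patient has to fail. Lesion length may add to this, since the protocol sets no limit per lesion.

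If the two trials differ in lesion burden, the difference in TLF partly reflects that burden. Fewer or shorter lesions in JNIR would favour non-inferiority; more or longer lesions would penalize JNIR. The imbalance could also go unseen, because the lesion and procedure tables in SAP 13 and 14 are not described as comparisons with matched BIONICS patients.

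A related gap is that six of the angiographic covariates (all but SYNTAX score) describe a lesion, while the propensity score is per patient. The SAP gives no rule for a patient with several target lesions.

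**Working it through.** **Inputs from the documents.** Margin 0.05; one-sided alpha 0.10; TLF rate 0.058; 4:1 matching; 100 JNIR patients with 5% loss (Protocol 7.5; SAP 8.5 and 15.1.2). Evaluable numbers are 100 × 0.95 = 95 JNIR and 4 × 95 = 380 BIONICS. Maximum target lesions are 2 vessels × 2 lesions = 4.

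**Inputs that must be assumed.** Neither document gives lesion counts or per-lesion risks for JNIR or BIONICS. The illustration takes every patient to have one or two lesions, independent lesions, and no relation between lesion count and the matched covariates. It treats lesion count only. Length is not quantified, because that would need a risk per millimetre that the documents do not give.

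**Step 1: the plan's error rate without bias.** With a BIONICS rate of 5.8%, a JNIR rate of 10.8% (exactly at the margin), 95 v 380 patients and the Farrington-Manning restricted variance, summing the exact binomial probabilities gives a type I error of 10.1%. This agrees with the nominal 10%.

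**Step 2: shift in TLF if all risk is lesion-driven.** Let f be the share of two-lesion patients and take 5% risk per lesion.

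TLF = 0.05(1 − f) + f(1 − 0.95²) = 0.05 + 0.0475f

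- f = 0.10: 5.48%
- f = 0.20: 5.95%
- f = 0.30: 6.43%

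A 10-point gap in f moves TLF by 0.0475 × 0.10, about 0.48 points. A 20-point gap moves it by 0.95 points, which is 0.95/5 = 19% of the margin.

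**Step 3: shift if about half the risk is lesion-driven.** Take a 2.5% patient-level risk that does not depend on lesion count, plus 2.5% per lesion.

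Shift = 0.975 × 0.975 × 0.025 × (gap in f) = 0.0238 × (gap in f)

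This gives 0.24 points for a 10-point gap and 0.48 points for a 20-point gap.

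**Step 4: recalibration.** If the risks are instead set so that BIONICS TLF is 5.8% with 20-40% two-lesion patients, gaps of 10-20 points give 0.2-0.5 points (half lesion-driven) or 0.4-0.9 points (all lesion-driven). The picture is the same.

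**Step 5: effect on the test if JNIR has fewer lesions.** The like-for-like difference is at the margin, but the observed JNIR rate is lower by the shift. Exact type I error, as in step 1:

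| Shift (points) | Type I error |
|---|---|
| 0 | 10.1% |
| 0.20 | 11.2% |
| 0.48 | 12.8% |
| 0.95 | 15.8% |

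**Step 6: effect if JNIR has more lesions.** Type I error falls below 10% and power is lost. By the SAP's printed unpooled formula, power goes from 72.0% to about 56-69% over the shifts in step 4. That the starting value differs from the plan's stated 80% is a separate matter and is not used here.

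**The case against.** The strongest reply is that this is possible residual confounding, not a demonstrated error. No figure in either document shows a difference in lesion burden. Protocol 7 says that JNIR uses inclusion and exclusion criteria similar to those of BIONICS, and JNIR caps vessels, lesions and stent length. All of that stands. A reader might infer that Japanese operators treat fewer or shorter lesions and that the comparison is therefore tilted towards non-inferiority. The documents support neither the premise nor the direction.

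Second, SYNTAX score is in the model and may carry part of the burden. Exclusion criterion 37 also bars patients with another lesion that needs, or probably will need, PCI within 12 months, which should tie overall disease more closely to the declared target lesions. So it would be too strong to say that lesion burden is wholly unmatched. Neither document says how SYNTAX is scored, so how much it captures cannot be judged from them. It is not listed as a count or length of target lesions.

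Third, TLF also includes cardiac death and target-vessel MI, and not all of that risk need scale with lesion count. Protocol 21.1 counts deaths as cardiac unless a non-cardiac cause is unequivocal. This is why the half-lesion-driven case is shown; the all-lesion-driven case is the upper end of the illustration.

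Fourth, a change has costs. The list also stands in Protocol 7.2.1, and the revision summary says that Section 7 was revised to the approach requested by PMDA. BIONICS enrollment ended in August 2015 and the SAP is dated August 2018, so one-year follow-up of the controls was already due, and a late change of covariates needs care over prespecification. Lesion count and length are site-reported, whereas the angiographic covariates come from QCA. These points shape the fix but do not remove the reason for it.

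Finally, a reader might infer that the model cannot be fitted at all because lesion-level covariates have no patient-level rule. That goes too far. LAD location reads naturally as yes or no, and the others need a stated convention. It is missing detail.

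**Conclusion.** The concern holds in a limited form. The thirteen covariates do not directly include target-lesion number or length, one failing lesion out of up to four is enough for TLF, and no other analysis controls for or displays the difference. Any JNIR-BIONICS gap in lesion burden would bias the primary comparison except as far as SYNTAX score or other matched covariates absorb it.

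The size and direction are unknown. The illustrated shifts, about 0.2 to 0.95 points against a 5-point margin, rest on an assumed 10-20 point gap in two-lesion patients, independent lesions, and no capture by the matched covariates. Under those assumptions, with fewer lesions in JNIR, one-sided type I error is about 11-16% instead of 10%. This is worth correcting because the items are baseline data already collected in JNIR. It does not show that the planned result would be wrong.

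**What to change.** Before the BIONICS comparison is run, and without reference to outcomes:

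1. Add the number of declared target lesions and the total target-lesion length per patient to the propensity model, provided BIONICS recorded them comparably. Use the declared count rather than the treated count, so that the covariate is fixed before treatment. Use the same data source in both trials, with core-laboratory length if available.
2. State how each lesion-level covariate becomes one value per patient, for example maximum stenosis, minimum reference diameter, any moderate or severe calcification or tortuosity, lowest TIMI flow, and any LAD lesion.
3. Report balance on the added items between JNIR and matched BIONICS, for example as standardized differences.

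The cost is two more terms in a model with about 100 JNIR patients, plus a matching change to Protocol 7.2.1 or an entry in SAP 4.3. If the sponsor must keep the agreed thirteen-covariate list as primary, run the extended model as a prespecified sensitivity analysis and still report balance on the two items.
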